13.5 Interim Analysis for Sample Size Re-estimation

We plan to conduct a sample size re-estimation when 35-40% of the participants have reached the primary endpoint. The goal of the analysis will be to estimate the intra-class correlation (ICC), as misspecification of the ICC in the original sample size calculations will impact study power. The analysis will be performed without estimating the treatment effect. If the results of the analysis suggest a modification to the sample size, the modifications will first be to the number of participants within a cluster (i.e., hospital) before consideration for modifying the number of clusters. The timing of the sample size re-estimation will be impacted by the rate of participant recruitment and when the hospitals initiate study enrollment. If these factors suggest an analysis may not yield useful results (e.g., half the hospitals have complete outcomes and the remaining hospitals do not have any outcomes), a sample size re-estimation may not be performed. Decisions related to performing the sample size re-estimations, and any suggested modifications to the sample size, will be made after careful review by study leadership, NIDA, and the DSMB.

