13.0 STATISTICAL ANALYSIS

13.1 General Design

13.1.1 Study Hypotheses

Hypothesis 1a

The new testing algorithm will increase the proportion of individuals who have completed all tests to confirm HIV diagnosis and received counseling within 30 days of screening HIV-positive, given they have screened HIV-positive on the initial EIA, from 23% to at least 50% (primary outcome).

Hypothesis 1b

The new testing algorithm will increase the proportion of individuals with a CD4 ≤350 cells/mm³ who initiate ART within 90 days of screening, given that they have screened HIV positive on the initial EIA (secondary outcome).

Hypothesis 1c

The effectiveness of the new testing algorithm will yield no significant differences for DUs at 1-month follow-up on testing completeness and at 3-month follow-up on ART treatment initiation, compared to non-DUs.

Hypothesis 2

The new testing algorithm will increase the proportion of individuals with a $VL \le 200$ copies/mL at 12 months, given that they have screened HIV positive on the initial EIA (tertiary outcome).

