13.2 Rationale for Sample Size and Statistical Power

We have selected a sample size of 180 HIV-positive participants (including approximately 10% DUs) in the control arm and 180 (including approximately 10% DUs) in the intervention arm, across 12 clusters (n=30 individuals in each cluster). This sample will achieve 93% power

based on a one-sided test (alpha=0.05) to detect a difference between the group proportions of 0.28, where under the alternative hypothesis the intervention group proportion is assumed to 0.50 and the control group proportion is assumed to be 0.22. This calculation assumes an intracluster correlation (ICC) within hospitals of 0.082 based on preliminary data. To assess the sensitivity of these calculations based on the 12 clusters and 30 patients per cluster, we examined in the table below effect sizes of 0.28, 0.33, and 0.38 and ICC estimates of 0.072, 0.082, and 0.092, assuming a one-side test at alpha=0.05 and the SOC success rate of 0.22.

		Intra-cluster correlation (ICC)		
		0.072	0.082	0.092
Success rate in One4All	0.50 (delta=0.28)	95.2%	93.6%	92.0%
	0.55 (delta=0.33)	98.8%	98.2%	97.5%
	0.60 (delta=0.38)	99.8%	99.7%	99.5%

Power calculations were also performed for the secondary outcome of initiating ART within 90 days and having a CD4 count \leq 350, among all the HIV-screened positive study participants. Data from preliminary data in Guangxi showed that 14% of HIV screened positive patients had CD4 counts \leq 350 and initiated ART within 90 days. We will have 93% power to detect an increase to 40% in the intervention group of initiating ART with CD4 \leq 350 within 90 days. For these calculations, we used an ICC of 0.082 and a one-sided test at alpha=0.05. All power calculations were performed by the PASS (Version 8) software.

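### Section 13.5 does not keep the arm difference out of the interim ICC; read naturally, it lets the hypothesised effect about double the estimate and signal a power shortfall that does not exist

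*Protocol*

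**What the plan says.** Protocol section 13.5 schedules a sample size re-estimation when 35-40% of participants have reached the primary endpoint. Its purpose is to estimate the ICC, because a wrong planning value would affect power. On the model it says only: "The analysis will be performed without estimating the treatment effect". If a change is indicated, "the modifications will first be to the number of participants within a cluster (i.e., hospital) before consideration for modifying the number of clusters". The section gives no target power, no cap on enrolment and no ICC threshold. The re-estimation may be skipped if it would not be informative, and any change goes to study leadership, NIDA and the DSMB for review.

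The quantity to be checked comes from section 13.2: "This calculation assumes an intracluster correlation (ICC) within hospitals of 0.082 based on preliminary data". There the ICC sits beside separate arm rates: "the intervention group proportion is assumed to 0.50 and the control group proportion is assumed to be 0.22". The planning ICC is therefore net of the arm difference. Sections 9.1 and 9.3 make the hospital the unit of randomisation, with six hospitals per arm.

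**The concern.** Every patient in a hospital belongs to the same arm. A random-hospital model without an arm term has nowhere to put the arm difference except the between-hospital variance. The resulting ICC is a different quantity from the 0.082 in section 13.2, and comparing the two misleads.

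The error depends on the treatment effect: the better One4all works, the larger the apparent ICC and the greater the apparent loss of power. The response could be extra patients or hospitals that are not needed. A large arm-free ICC is also indirect evidence of an effect, and it would be seen by study leadership and the funder, whom the sentence presumably meant to keep unaware of it.

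A separate question is how far the first remedy works if the ICC, real or apparent, is high. Adding patients to a fixed number of hospitals has a ceiling.

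**Working it through.** **Inputs (Protocol 13.2, 13.5, 9.3).** Rates 0.22 and 0.50; one-sided alpha 0.05; 6 hospitals per arm, 30 patients each; ICC 0.082 with a grid of 0.072 to 0.092. The interim falls at 35-40% of 360, that is 126 to 144 patients, or about 11 to 12 per hospital.

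**Step 1. Reproduce the stated power.** The protocol names PASS 8 but prints no formula. I used a two-proportion z-test with unpooled variance and a design effect:

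- n_eff per arm = 180 / (1 + 29 × 0.082) = 180 / 3.378 = 53.3
- Sum of variances = 0.22 × 0.78 + 0.50 × 0.50 = 0.4216
- Power = Φ(0.28 / √(0.4216 / 53.3) − 1.645) = 93.4%

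The protocol says "This sample will achieve 93% power", and its table gives 93.6%. At ICC 0.072 and 0.092 the formula gives 95.0% and 91.6% (table: 95.2% and 92.0%). The agreement is close enough to use.

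**Step 2. ICC with no arm term, true within-arm ICC 0.082.**

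- Mean within-arm variance W = 0.4216 / 2 = 0.2108
- Between-hospital variance within arm = 0.082 × 0.2108 = 0.0173
- Added by the arm difference = (0.28 / 2)² = 0.0196
- Total variance at the mean rate = 0.36 × 0.64 = 0.2304
- Arm-free ICC = (0.0173 + 0.0196) / 0.2304 = 0.160, or 1.95 times 0.082

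With the finite-sample factor 12/11 on the arm component, the ANOVA expectation is 0.167. Using the 23% control rate of Hypothesis 1a gives 0.154 (ANOVA 0.160).

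**Step 3. Simulation.** Beta-binomial hospitals, 12 hospitals × 12 patients, true ICC 0.082, ANOVA estimator, 20,000 runs:

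| True rates | Arm in model | Mean ICC | Above 0.092 |
|---|---|---|---|
| 0.22 v 0.50 | no | about 0.166 | about 80% |
| 0.22 v 0.50 | yes | about 0.081 | about 40% |
| 0.22 v 0.60 | no | about 0.228 | about 94% |
| 0.22 v 0.22 | either | about 0.079 | about 38% |

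The inflation disappears when there is no effect and grows with the effect. With arm in the model at 0.22 v 0.50, the central 95% range of the estimate is still about −0.03 to 0.24.

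**Step 4. What more patients per hospital can do.** With unlimited patients, n_eff per arm tends to 6 / ICC. For 93% power n_eff must be 52.4, so the ICC must be below 6 / 52.4 = 0.115. Pooled-variance and t-based versions of the test put this limit between 0.099 and 0.115.

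| ICC | Patients per hospital | Power |
|---|---|---|
| 0.092 | 41 | 93.1% |
| 0.100 | 62 | 93.0% |
| 0.160 | 30 | 78.6% |
| 0.160 | about 41 | 80% |
| 0.160 | 60 | 81.3% |
| 0.160 | unlimited | 84.0% |

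At ICC 0.160 with 30 per hospital, 93% would need about 10 hospitals per arm. The arm-free estimate exceeds 0.115 in about 71% of the simulated interims at 0.22 v 0.50.

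**The case against.** The strongest objection is that section 13.5 never says arm is left out of the ICC model. An ICC computed separately in each arm and averaged, with no contrast formed, would fit the sentence and avoid the inflation, and the interim model could be specified in the statistical analysis plan. This stands in part: the omission is a reading, though the natural one, because the sentence is the only instruction given and an arm-adjusted model does estimate an arm effect.

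A reader might also infer that enlarging hospitals cannot restore power. The documents do not support that. It works at 0.092, the highest ICC the protocol considered, and reaches 80% even at 0.16. Section 13.5 sets no target power for the re-estimation; 93% is the section 13.2 figure. It also already allows a change in the number of hospitals as a second step.

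Nor does a rule trigger anything automatically. There is no threshold, three bodies review any change, and the exercise may be skipped. That safeguard stands, but the figure under review would itself be inflated.

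Finally, a reader might infer lost power or a biased result. Neither follows. If only the arm effect inflates the ICC, the true value is still 0.082, power is still about 93%, and the final effect estimate is untouched.

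**Conclusion.** The point holds as a defect of wording with a calculable consequence. Read as a model without an arm term, section 13.5 produces an ICC of about 0.16 to 0.17 where the comparable planning value is 0.082. At 30 per hospital that would be read as power of about 79% instead of 93%. The harm is a false alarm: possible needless enrolment or extra hospitals, and an indirect hint of the effect.

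Separately, the order of remedies is sound for a modest rise in the ICC. Above about 0.115 it cannot return power to 93%, and the section does not say so.

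These figures assume the section 13.2 rates and ICC, equal hospital sizes at the interim, beta-binomial variation between hospitals and the z approximation. The doubling does not depend on the power formula.

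**What to change.** Amend section 13.5 in two places.

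1. State that an independent or DSMB statistician estimates the ICC within arm, or with arm and stratum as nuisance fixed effects, and releases only that ICC and its interval, with no arm means or contrast.
2. State the target power, and that per-hospital enrolment is raised only where the power calculation at the estimated ICC shows that this reaches the target. Otherwise the stated power is updated, or the change in the number of hospitals that the section already permits is considered.

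The cost is a few sentences and no change to trial procedures. The independent statistician must handle arm codes, while leadership stays blind to the effect. The correction removes the inflation but not the imprecision: with 12 patients per hospital and a true ICC of 0.082, the adjusted estimate still exceeds 0.092 about 40% of the time. Any decision should therefore weigh the interval as well as the point estimate.

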13.6 Missing Data and Dropouts

The outcome is the completeness of the endpoints (i.e., receipt of post-test counseling following providing results of testing to the participant and ART initiation). Dropouts and missing data indicate that the endpoints were not successfully reached. There will be no special treatment for missing values.

13.7 Demographic and Baseline Characteristics

Baseline demographic and clinical characteristics will be summarized for each arm. Distribution, frequency, and percentage will be checked for discrete variables. Distribution, mean, median, and range will also be checked for continuous variables. The balance of the intervention and control group will be checked by statistical tests such as a Chi-squared test, Fisher's exact test, or Wilcoxon test.

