2.0 STUDY SYNOPSIS AND SCHEMA

Study Objectives

This study will evaluate the effects of a comprehensive diagnostic approach to enhance the percentage of participants that receive their HIV testing results and counseling, given they are HIV positive on the initial EIA screening. All enrolled participants will be followed for 12 months with the viral load (VL) measured at that time point in addition to the status of any HIV treatment they have received.

Study Design

The study consists of a cluster randomized trial (CRT) at county hospitals in Guangxi, China to assess the effectiveness of a structural intervention: a new testing algorithm, consisting of rapid point-of-care (POC) HIV and CD4 testing, with viral load (VL) testing in parallel, designed to ensure completeness of diagnostic assessment and accelerate time to ART initiation for patients deemed ART eligible (hereafter called the One4all Test Intervention).

This CRT will be conducted in 12 county general hospitals with an estimated average of 30 participants per hospital, totaling an estimated 360 participants. The unit of randomization is the hospital. Hospitals will be randomized to 1) theOne4all Test Intervention, or 2) the control condition, consisting of the current standard of care (SOC). The efficacy of the intervention will be evaluated at 1, 3 and 12-month follow-up assessments, and the differential efficacy for drug users (DUs) and non-drug users will be examined, if an adequate number of DUs is enrolled.

Study Population

The study population will consist of adult participants who screen positive on an initial HIV enzyme immunoassay (EIA) in the 12 study hospitals. Since the study will be conducted in China, the vast majority of participants will be of Chinese or Asian descent. Women will be included and are expected to represent approximately 26% of the study population.

Eliqibility Criteria

Site Eligibility Criteria: The location of our study is Guangxi Zhuang Autonomous Region (Guangxi). We will select county-level general hospitals in order to ensure sufficient caseload at each hospital and homogeneity across hospitals. Guangxi counties usually have one general hospital (a limited number of counties have two or more general hospitals); this hospital has been designated as the only setting for delivering ART services in the respective county.

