9.3 Enrollment Procedures

Information on testing procedures and study data collection will be provided to each individual who presents for HIV screening via the Participant Handout (**Appendix B**) prior to HIV screening. Receipt of the handout will be documented. Participants with questions about the study may have their questions answered by designated local providers, CDC or NCAIDS staff. The 12 hospitals in the study will use one of two testing algorithms, with 6 hospitals randomly assigned to each algorithm. Each hospital will only offer HIV testing according to its assigned algorithm. Patients who screen positive on the initial EIA HIV screen will be enrolled in the study. Local hospital data will be protected per local hospital practices. Study data will be extracted and assigned an ID so that the data are de-identified; the participant's name will be scrubbed.

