13.1.3 Factors for Stratification and Covariate Adjustment

The study design is a cluster randomized clinical trial. Ideally, the randomization should ensure that the distribution of characteristics across the intervention and control groups is the same at baseline, thus not requiring adjustment of covariates for data analysis. However, in practice, randomization cannot guarantee complete balance between the intervention and control groups, especially since the randomization unit for this study is the hospital. A single stratified randomization creating two strata will be used to allocate hospitals to either the intervention group or the control group. Stratification will be based on historical rates of receipt of post-test results and counseling following testing completeness and will be included in the primary outcome statistical model. The correlation of participants within each hospital will also be adjusted. Other factors for covariate adjustment will be considered, such as participant-level variables including age at baseline, ethnicity, gender, primary drug use (injection drug use versus non-injection drug use, opiate versus non-opiate), and socioeconomic status and hospital-level characteristics such as number of hospital beds. Details on the process by which covariates will be considered in the statistical models are detailed in the study's Statistical Analysis Plan.

We use baseline completeness rates as a variable to stratify the 12 hospitals under SOC. Medical record review at the 12 hospitals was performed to serve as the basis for determining the stratification. Cases that were newly screened HIV positive between January 1, 2013 and June 30, 2013 from each of the 12 hospitals were assessed for completion of HIV confirmation and counseling within 30 days of initial HIV screening. The completeness rates of the 12 hospitals were ranked to establish the strata. Furthermore, the baseline completeness rate will be treated as the second level predictor variable in our multi-level (mixed) logistic regression analysis.

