13.3 Statistical Methods for Primary and Secondary Outcomes

13.3.1 Primary Outcome

Primary Analysis for Hypothesis 1a

Hierarchical regression models (e.g., mixed-effect models or random-effect models (48, 49)) will be used to compare the proportion of HIV-positive individuals who received a complete suite of test services, results and post-test counseling within 30 days between individuals assigned to the One4all Test Intervention arm (i.e., individuals who receive a new testing algorithm, consisting of HIV, CD4, and VL tests) and individuals receiving SOC in the control arm. Specifically, proportions will be compared using logistic regression with hospital-level random effects to account for potential ICC within hospitals. Models that do not account for ICC will underestimate standard errors. Testing completeness rates will be compared at 30 days after being screened HIV-positive in the hospital. In addition to the inclusion of a covariate for the intervention arm (1=intervention, 0=SOC), random effect logistic regression models will control for the stratification factor and potential confounding variables, including age, gender, transmission mode, drug use, and other characteristics that are found to differ at baseline.

Secondary Analyses for Hypothesis 1a

A secondary analysis of primary endpoint will also be performed: comparison between the time from initial EIA positive screen to completion of testing between the two treatment groups, not

restricted to the 30 days period. Participants who did not complete testing will be censored at the endpoint of the study. Kaplan-Maier will be used to compare time differences by days from the positive HIV screening to the receipt of post-test counseling (can extend beyond the 30 day cut point period) between the intervention and control groups. An extended Cox model accounting for the effects of clustering will be used to calculate the intervention effect by hazard ratios while controlling for other covariates. Further, testing completeness will be compared between the two treatment groups at additional thresholds of 45, 60, and 90 days, analyzing these endpoints in a similar fashion to the primary analysis.

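### The baseline balance tests ignore the randomisation of hospitals and, on the natural reading, would choose the additional covariates of the primary model

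*Protocol*

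**What the plan says.** Protocol section 2.0 states "The unit of randomization is the hospital", and section 9.3 gives the allocation as two algorithms "with 6 hospitals randomly assigned to each algorithm". Section 13.2 plans 180 participants per arm "across 12 clusters (n=30 individuals in each cluster".

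On baseline comparability, section 13.7 says: "The balance of the intervention and control group will be checked by statistical tests such as a Chi-squared test, Fisher's exact test, or Wilcoxon test". It names neither the unit of analysis nor a significance level, and does not mention clustering.

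Section 13.3.1 specifies the primary analysis as a logistic regression with hospital random effects. Besides arm and the stratification factor, it controls for "potential confounding variables, including age, gender, transmission mode, drug use, and other characteristics that are found to differ at baseline". The same paragraph warns that a model that leaves out the ICC gives standard errors that are too small.

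Section 13.1.3 says that "randomization cannot guarantee complete balance between the intervention and control groups, especially since the randomization unit for this study is the hospital". It refers the details of how covariates will be considered to the SAP, which is not available here.

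**The concern.** Two things go wrong together.

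First, the reference distributions of the ordinary chi-squared, Fisher and Wilcoxon tests assume that 360 individuals were allocated independently. Twelve hospitals were allocated. If patients in the same hospital resemble each other in ethnicity, education or occupation, arm differences vary more than these tests allow. They then signal imbalance too often when the randomisation worked exactly as designed. This is the fault that section 13.3.1 warns of for the outcome.

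Second, the result does not stay in the baseline table. Section 13.3.1 admits further covariates to the primary model because they differ at baseline, and section 13.7 is the only place that describes how differences are looked for. Part of the primary model would therefore be settled after seeing the data, by a miscalibrated test and not by whether the covariate predicts the outcome. At stake are a baseline table that may wrongly suggest failed randomisation and a primary model that is not fully fixed in advance.

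**Working it through.** **Inputs.** 6 hospitals per arm (section 9.3); 30 participants per hospital (13.2); "an intracluster correlation (ICC) within hospitals of 0.082 based on preliminary data"; planning rates where "the intervention group proportion is assumed to 0.50 and the control group proportion is assumed to be 0.22"; one-sided alpha 0.05 for the endpoints (13.4). The ICC refers to the primary outcome; no ICC is given for any baseline characteristic. No alpha is given for the balance tests, so a two-sided 5% level is assumed.

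**The protocol's own power figure first.** Design effect = 1 + (30 − 1) × 0.082 = 3.378. Effective sample size per arm = 180 / 3.378 = 53.3. Standard error = √[(0.22 × 0.78 + 0.50 × 0.50) / 53.3] = 0.089. Power = Φ(0.28 / 0.089 − 1.645) = 93.4%. The protocol states 93% in the text and 93.6% in the table, so the design-effect formula matches its planning.

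**False-alarm rate of a test that ignores clustering.** With no true difference, the naive test statistic has variance equal to the design effect, not 1. Hence

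rate = 2 × [1 − Φ(1.96 / √(1 + 29 × ICC))].

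This was checked by simulation under no arm difference: beta-binomial data for chi-squared, Fisher and a t test on the 12 hospital proportions (20,000 runs, prevalences 26% and 10%), and normal random-intercept data for Wilcoxon (4,000 runs).

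| Assumed baseline ICC | Design effect | Formula | Chi-squared | Fisher | Wilcoxon | Hospital-level t test |
|---|---|---|---|---|---|---|
| 0 | 1.00 | 5.0% | 4.8-5.3% | 3.1-4.0% | 5.0% | 5.1-5.2% |
| 0.01 | 1.29 | 8.4% | 8.5-8.8% | 6.0-7.0% | 7.8% | 5.0-5.1% |
| 0.02 | 1.58 | 11.9% | 11.8-12.1% | 9.0-9.7% | 12.3% | 4.7-4.8% |
| 0.05 | 2.45 | 21.1% | 20.7-21.6% | 16.9-18.7% | 21.1% | 4.4-5.0% |
| 0.082 | 3.378 | 28.6% | 28.5-28.6% | 24.2-25.7% | 28.6% | 4.4-4.9% |

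Inverting the formula, a rate of 20% needs a baseline ICC of about 0.046, and a rate of 30% about 0.089.

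**What is open to selection.** Of the baseline items in section 9.4, age, gender, transmission route and drug use are in the model whatever the tests show. Marital status, ethnicity, education, occupation, sexual risk behaviour and clinical symptoms remain, roughly five or six candidates. For five independent ones, the chance that at least one is flagged is 1 − (1 − rate)⁵: 23% with no clustering, 47% at ICC 0.02, 69% at 0.05 and 82% at 0.082. Correlated characteristics would change these figures.

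**Effect on power.** One simulation (1,000 replicates, random-intercept logistic model, covariate ICC 0.082) forced four covariates in and left two to test-based selection. It assumed three prognostic covariates, two of them among the forced four, and omitted the stratification factor. At the planned effect, log odds ratio ln[(0.50/0.50) / (0.22/0.78)] = 1.27, power under the protocol's rule against a fixed prognostic list was:
- 94.1% against 94.8% when the covariates had no link to hospital variance
- 94.8% against 95.9% when they explained half of it

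At a smaller log odds ratio of 1.0 the figures were 80.5% against 81.1%, and 81.8% against 84.4%. The Monte Carlo standard error of a power near 94-96% with 1,000 replicates is about 0.6 to 0.8 point (for example √(0.948 × 0.052 / 1,000) = 0.7 point). The gaps at the planned effect are therefore small and imprecise.

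**The case against.** The strongest reply has four parts.

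- **The link is not written out.** Section 13.7 says nothing about covariate selection, section 13.3.1 names no test or p-value, the list of tests is only illustrative, and section 13.1.3 leaves the process to the SAP. This stands in part: the link and the participant-level unit are inferences. But a rule admitting covariates because they differ at baseline is written in the protocol, and chi-squared or Fisher tests of participant characteristics hardly fit a comparison of 6 hospitals with 6. A SAP that followed both sections would inherit the problem.
- **Most of the adjustment is fixed.** This stands. A reader might infer that the tests choose the whole covariate set and that important predictors could be dropped for looking balanced. The four named covariates and the stratification factor enter regardless, so selection affects only the additional ones.
- **The size is unknown.** This also stands. A reader might take a false-alarm rate of 20-30% as a property of this trial. The protocol's only ICC belongs to testing completeness, which depends on hospital processes; demographic variables may cluster less. Nor does section 13.7 say that a hospital attribute such as bed count would be tested on patients, so no figure for that case belongs here.
- **A balance check has a use.** Participants enter after hospitals are allocated, so a look for differential recruitment is reasonable. Descriptive summaries by arm and hospital serve that purpose. A test that ignores clustering cannot separate recruitment bias from ordinary variation between hospitals.

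**Conclusion.** The point holds in a limited form. As named, the tests in section 13.7 do not respect the unit of randomisation and exceed their nominal level at every non-zero baseline ICC tried. The excess is about 8-12% in place of 5% at ICC 0.01-0.02, 21% at 0.05, and 29% if baseline variables cluster like the outcome, with Fisher's test somewhat lower. These figures rest on an assumed two-sided 5% level, 30 participants per hospital and an assumed baseline ICC.

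The consequence is a potentially misleading baseline table and a primary model whose additional covariates depend on the realised data. A material loss of power might be inferred, but the documents do not support it: with the named covariates forced in, the loss was about 1 point at the planned effect under one set of assumptions. Nor is there a basis for claiming extra type I error. The change is worth making because it is almost free, not because the primary conclusion is in danger.

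**What to change.** In section 13.7, replace the significance tests with descriptive summaries by arm and by hospital, with standardised differences if wanted. If a test is kept, use the hospital as the unit (for example a comparison of the 12 hospital summaries or a permutation of hospitals), and do not let it drive the primary model.

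In section 13.3.1, delete the open-ended last item of the covariate list. Fix the primary model in advance as arm, the stratification factor and the named covariates: age, gender, transmission mode and drug use. Make any adjustment for an observed imbalance a labelled sensitivity analysis, and bring section 13.1.3 and the SAP into line before database lock.

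The cost is a sentence or two in each section, with no additional data or participants. The downside is that a chance imbalance in an unlisted characteristic is handled only in the sensitivity analysis.
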